### 12.2 Data Analysis

Analysis of collected data is based on descriptive statistics including absolute and relative frequencies of discrete variables. Continuous variables are described by count (without missing), mean and its 95% confidence interval (CI), standard deviation, median, minimum, and maximum. Discrete variables are described by count (absolute frequency), and percentages (relative frequency).

Missing data will not be replaced.

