### 7.2 Secondary endpoints

- Proportion of relapse-free patients at 24 and 48 months
- ARR at 24 months
- The time to sustained progression of disability from baseline up to 24 and 48 months
- Time to the first relapse from baseline up to 48 months
- Time to the second relapse from baseline up to 48 months

- Changes in mean number of T1 Gd+ lesions per MRI scan taken at 12, 24, 36 and 48 months compared to baseline
- Changes in mean number of active T2-weighted lesions per MRI scan taken at 12, 24, 36 and 48 months compared to baseline
- Changes in level of disability as measured by EDSS at 6, 12, 18, 24, 30, 36, 42 and 48 months compared to baseline
- No evidence of disease activity (NEDA-3) at 24 and 48 months
- The proportion of patients receiving rescue therapy according to local standards of care from baseline up to 48 months
- Patient adherence to Cladribine 10 mg tablets treatment after both dosing periods as assessed at 3 and 15 months (by counting used tablets from original packages as patients will be asked to bring them to the site).
- Frequency of adverse events interviewed or reported spontaneously by the patients or as noted on physical, MRI or laboratory examinations up to month 48
- Percentage of patients with at least 1 Common Terminology Criteria for Adverse Events (CTCAE) grade 3 or 4 Lymphocyte Toxicity up to month 48
- Median time to recovery from grade 3 or 4 Lymphocyte Toxicity
- Percentage of patients who developed herpes zoster infections or malignancies up to month 48

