## 12 STATISTICAL METHODOLOGY

Based on this part of the protocol, a statistical analysis plan (SAP) will be created. The statistical analysis plan will be processed and approved before closing the database. Possible changes in the evaluated parameters or in the methods of analysis against the protocol will be described and justified in SAP. The statistical analysis is performed in IBM SPSS software.

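### Section 12.2 makes no exception to its mean/SD summary for time to first relapse, second relapse and sustained progression; applied as written, it averages only patients who had the event

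*Protocol*

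**What the plan says.** Section 7.2 lists three relapse or progression times among the secondary endpoints: "Time to the first relapse from baseline up to 48 months", "Time to the second relapse from baseline up to 48 months" and "The time to sustained progression of disability from baseline up to 24 and 48 months". A fourth time, recovery from lymphocyte toxicity, is already named there as a median.

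Section 12.2 is the whole of the data analysis text. It opens with "Analysis of collected data is based on descriptive statistics including absolute and relative frequencies of discrete variables". It then recognises two classes of variable, continuous and discrete, and gives one summary for each. For the first class: "Continuous variables are described by count (without missing), mean and its 95% confidence interval (CI), standard deviation, median, minimum, and maximum". It closes with "Missing data will not be replaced". The Protocol Summary repeats these rules. Neither place mentions censoring or a survival estimate, and neither sets the time-to-event endpoints apart.

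Section 12 ties the later plan to this text: "Based on this part of the protocol, a statistical analysis plan (SAP) will be created". Changes of method against the protocol are allowed there, but must be described and justified.

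**The concern.** A time in months is a continuous quantity, and Section 12.2 offers it only one summary. A patient followed to month 48 without a relapse has no relapse time. With a non-missing count, no replacement and no censoring rule, the only instruction an analyst has is to summarise the observed times.

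The mean or median of those times is conditional on the event having happened inside the window. It says little about how soon or how often events occur in the treated population. If the rate is low, event times spread almost evenly over the window and the mean approaches half of it, 48/2 = 24 months, whatever the rate. A reader could take a reported median near 21 months to mean that half the patients had relapsed by then, when most had not relapsed by month 48.

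**Working it through.** **Inputs.** Supposed relapse rate 0.14 per year and 85 evaluable patients (Section 12.1); four years of follow-up (Section 5.1). The protocol gives no figure for any time-to-event endpoint, so there is none to reproduce. The enrolment target does reproduce: 85/(1 − 0.15) = 100. The power statement in Section 12.1 is a separate matter and is not used here.

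**Assumptions (not in the protocol).** Constant rate r, relapses following a Poisson process, complete follow-up to T = 4 years. The rates 0.07 and 0.28 are half and double the protocol's figure.

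**First relapse.**
- Share with an event: P1 = 1 − exp(−rT). At 0.14: 1 − exp(−0.56) = 1 − 0.571 = 0.429, or about 36 of 85. The other 57% have no time to average.
- Mean among those with an event: 1/r − T·exp(−rT)/P1. At 0.14: 7.143 − 4 × 0.5712/0.4288 = 1.814 years = 21.8 months.
- Median among those with an event: −ln(1 − P1/2)/r. At 0.14: 0.2413/0.14 = 1.724 years = 20.7 months. The median over all patients is ln 2/0.14 = 4.95 years = 59.4 months, beyond the window.
- Restricted mean over 48 months, counting everyone: P1/r. At 0.14: 0.4288/0.14 = 3.06 years = 36.8 months.

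| Rate per year | With first relapse | Mean among those with a relapse | Relapse-free at 48 months | Restricted mean, all patients |
|---|---|---|---|---|
| 0.07 | 24.4% | 22.9 months | 75.6% | 41.9 months |
| 0.14 | 42.9% | 21.8 months | 57.1% | 36.8 months |
| 0.28 | 67.4% | 19.6 months | 32.6% | 28.9 months |

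A fourfold change in the rate moves the mean among relapsers by 22.9 − 19.6 = 3.3 months. The relapse-free proportion moves by 75.6 − 32.6 = 43 percentage points, and the restricted mean by 41.9 − 28.9 = 13.0 months.

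**Second relapse.** P2 = 1 − exp(−rT)(1 + rT). At 0.14: 1 − 0.5712 × 1.56 = 0.109, or about 9 of 85. The mean time among those patients is 31.2, 30.5 and 28.8 months at rates 0.07, 0.14 and 0.28.

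**Sustained progression.** The protocol gives no expected risk. Assuming a 48-month risk of 10%, 20%, 30% or 40%, r = −ln(1 − risk)/4 and the mean formula above give 23.6, 23.1, 22.6 and 22.0 months.

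**Sensitivity, first relapse.** Means among relapsers at 0.07, 0.14 and 0.28, by simulation:
- patient-level gamma variation in the rate (variance 1): 22.0, 20.5 and 18.1 months;
- 15% of patients leaving at uniformly distributed times: 22.3, 21.2 and 19.0 months.

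The flat pattern does not depend on equal risk across patients or on complete follow-up.

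**The case against.** The strongest objection is that this is an inference. Section 12.2 does not call these endpoints continuous, and it does not say that an event-free patient counts as missing. Declining to replace missing data rules out imputation, not censoring. A Kaplan-Meier curve is itself descriptive. Censoring rules are commonly left to the SAP, which is not among the documents reviewed, and Section 12 lets it change methods. Section 12.2 is also not exhaustive: it gives no method for the adherence and relapse association listed in Section 4.2.

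Most of this stands. A reader might infer that the sponsor has decided to drop event-free patients; the text does not say so. What remains is that Section 12.2 is not simply silent. It states a general rule without exception, and Section 12 makes any other method a departure to be justified.

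Three wider readings are tempting and are not supported.
- *Median time to lymphocyte recovery is too short because the last count is at V6.* V6 is only the last scheduled count in Table 8-1. Grade 3 or 4 lymphocyte toxicity is an adverse event of special interest (Section 11.1), events are recorded with follow-up to the end-of-study or withdrawal visit (Section 11), and Section 11.2.2 requires follow-up to resolution or permanence. Recovery can therefore be captured later. With an assumed true median of 6 months, the median among recovered patients is 4.1 months under 12 months of observation but 5.9 under 36.
- *The relapse-free proportions are wrong too.* They are discrete and fall outside the quoted rule.
- *The study loses its information on event frequency.* The annualized relapse rate, the relapse-free proportions and NEDA-3 are all reported separately.

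**Conclusion.** The point holds for three secondary endpoints: time to first relapse, time to second relapse and time to sustained progression. Applied as written, Section 12.2 summarises only patients with the event. At a constant 0.14 per year, about 43% contribute to the first relapse and about 11% to the second, and the result is set mainly by the 48-month window. These percentages rest on the constant-rate Poisson assumption; the insensitivity of the mean also holds under the two departures checked. The progression figures rest on assumed risks.

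The primary endpoint is not affected. The rule should be corrected before analysis, but it does not threaten the study's main result.

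**What to change.** State in Section 12.2 that the three endpoints are exempt from the mean/SD summary and are described by Kaplan-Meier. Event-free patients are censored at their last assessment. Report event-free proportions with 95% CI at 24 and 48 months, and the median only if it is reached. Time to lymphocyte recovery may be handled the same way, censoring patients unrecovered at their last available count.

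One drawback should be stated alongside. Section 6.3.3 withdraws patients who start a new disease-modifying drug, and such a switch may follow disease activity, so censoring there may be informative. Report the number of these withdrawals and add a sensitivity analysis that counts them as events.

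The cost is one paragraph in Section 12.2, carried into the SAP. No extra data are needed: relapses, EDSS scores, visit dates and withdrawal reasons are already collected, and the named software provides Kaplan-Meier.

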### 12.3 Interim analysis

Interim analysis will be performed when all patients complete visit V7 or withdraw earlier.

## 13 ETHICAL ASPECTS

This project will be carried out in accordance with the principles set out at the 18th Meeting of the World Health Organization (Helsinki, 2013) and in all Appendices thereto and in accordance with the applicable legislation of the Slovak republic.

The Sponsor will provide all necessary registrations in compliance with the regulations, including data protection rules.

### 13.1 Informed Consent

Prior to any data collection under this protocol, the Informed Consent Form (ICF) must be signed by the patient, in accordance with local practice and regulations. Information about the study will be explained to the patient by the participating physician. A copy of the ICF, signed and dated by the patient, must be given to the patient. Confirmation of a patient's informed consent must also be documented in the patient's medical records prior to any data collection under this protocol.

The ICF must not be altered without the prior agreement of the relevant independent ethics committee (IEC) and Sponsor.

In order to ensure patient confidentiality, patients will be assigned a unique study number. The key, matching study numbers with patient names will be maintained by the site, and only the study numbers will be recorded on the data collection forms. The Investigator and local site staff will securely store information separately from other study information and it will not be provided to third parties.

### **13.2 Ethics Committee Approval**

Prior to the collection of any study related data, IEC approval of the protocol and ICF and will be obtained as applicable.

### **13.3 Compensation to Coordinating Investigator**

Coordinating Investigator will not receive any remuneration or compensation for work performed and time spent during the study conduct.

## **14 OTHER ASPECTS**

### **14.1 Record Archiving**

The participating physicians shall arrange for the retention of study documentation until the end of the study. In addition, the participating physicians will comply with specific local regulations/recommendations with regards to patient record retention

It is recommended that the participating physician retains the study documents at least fifteen years (15) after the completion or discontinuation of the study, unless otherwise specified in the Investigator Agreement in line with additional standards and/or local laws.

However, applicable regulatory requirements should be taken into account in the event that a longer period is required.

### **14.2 Data Protection and Confidentiality**

The patient's personal data and participating physicians' personal data which may be included in Sponsor database shall be treated in compliance with all local applicable laws and regulations.

When archiving or processing personal data pertaining to the participating physicians and/or to the patients, Sponsor shall take all appropriate measures to safeguard and prevent access to this data by any unauthorized third party.

In any presentations or in publications of the results of the study, the patients' identities will remain anonymous and confidential. Sponsor, its designee(s), and various government health agencies may inspect the records of the study. Every effort will be made to keep the patients' personal medical data confidential.

All materials, information (oral or written) and unpublished documents provided to the participating physician, including the current protocol and patient records, are the sole property of the Sponsor. These materials and information may not be provided or disclosed by the participating physicians or any person on their team to unauthorized persons without the prior written consent of the Sponsor.

The participating physician considers all information received, obtained or derived during the project to be confidential and will take all necessary steps to ensure that there is no breach of confidentiality, except for the information to be provided according to law.

### 14.3 Data Ownership and Publication Policy

All data generated from this study are the property of Sponsor who will establish a uniform procedure for analysing, publishing, and disseminating findings from this study.

No use of the data including any presentation or publication will be possible without the authorisation of Sponsor conducting the study.

### 14.4 Protocol Amendment

Amendments to the protocol can only be made by Sponsor in the written form. All protocol amendments must be signed and dated by the Coordinating Investigator and approved by IEC as applicable prior their implementation.

### 14.5 Premature Discontinuation of the Study

Sponsor can decide at any time and for any reason to prematurely stop or to interrupt the study; the decision will be communicated in writing to the Investigators.

Similarly, should the Coordinating Investigator decide to withdraw from the study, he will have to immediately inform Sponsor in writing.

In case of study premature discontinuation, all national applicable regulatory procedures will be followed.

